2.0 STUDY OBJECTIVES

The objective of the currently proposed study is to provide pilot data for this longer-term research program. In preparation for this K23 application, we must achieve the following aims.

Aim 1: Determine the cross-sectional prevalence of undiagnosed and uncontrolled hypertension within the Cedars-Sinai Health System, as well as the patient, physician, and clinic characteristics associated with these outcomes. This will document the presence and extent of problems at this institution and reveal which populations and settings are most affected, providing insights that can be used to develop and implement future interventions.

Aim 2: Develop and pilot test new time-to-care and time-to-control measures. These measures will evaluate (1) how long it takes from when evidence exists in the EMR that patients meet criteria for hypertension before clinicians document a diagnosis and initiate treatment, (2) how long evidence exists that control is suboptimal before clinicians intensify treatment, and (3) how long each of these conditions exists before goal blood pressures are achieved. We plan to use these new measures in our future work because we expect them to be more responsive to changes in care than cross-sectional measures of control would be, and because they include both care processes (i.e., did clinicians do the right things) and outcomes (i.e., were clinical goals achieved), making it possible to distinguish whether suboptimal control is due lack of recognition, lack of action (e.g., clinical inertia), or insufficient action (e.g., suboptimal adjustment of antihypertensive medications).

Aims 3A and 3B: Aim 3A – Assess the validity, responsiveness, and potential utility of the new time-to-care and time-to-control measures. To assess validity, we can examine whether performance on the new measures is associated with performance on cross-sectional measures of blood pressure control. To assess responsiveness and potential utility, we can examine how performance changes with clinical practice. For example, the introduction of the 2017 ACC/AHA guidelines represented a marked change in the standard of care for hypertension in terms of criteria for diagnosis and blood pressure goals. If the

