We will create three time-to-care measures: time-to-diagnosis, for patients who qualify for new diagnoses; time-to-initiate, for the same patients; and time-to-intensify, for patients with established diagnoses. We will create two time-to-control measures, one for patients with new and one for patients with established diagnoses. The new time-to-care and time-to-control measures will be based on the 2017 ACC/AHA guidelines. We will define undiagnosed hypertension as two ambulatory blood pressures \geq 130/80 without an ICD-9/10 code for hypertension in the preceding year; uncontrolled hypertension will be defined using the same blood pressure criterion but patients will have an ICD-9/10 code for hypertension. A new diagnosis of hypertension will be defined as an ICD-9/10 code for hypertension without a prior code or antihypertensive medication use in the preceding year. We will define treatment initiation as the first prescription for an antihypertensive medication following a new diagnosis of hypertension. Treatment intensification will represent the addition of another antihypertensive medication, an increase in the dose of an existing antihypertensive medication, and a change from one antihypertensive medication to another. We will access the 2017 guidelines and other standard sources to develop a list of antihypertensive medications. Time to care will be calculated as the number of days from the last blood pressure above goal to the documentation of the diagnosis or the initiation/intensification of treatment. Time to control will be calculated as the number of days from the last blood pressure above goal to the first blood pressure at goal.

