5.4 SOURCE DOCUMENTS

- For Aims 1, 2 and 3A, we seek to obtain the data in Tables 1 and 2 from the EMR with the assistance of the Research and Informatics Scientific Computing Core (RISCC)
 - Table 1 contains patient level data to be obtained at the visit level
 - Table 2 contains medications to be obtained at the patient level for each visit. Data is to include if the medication has been prescribed and if so, at what dose and frequency. The prescribing provider and providers specialty will also be acquired.
 - Zip Code will be used to estimate population level sociodemographic factors from census data
- For Aim 3B, patient medical records will be the source document for the information identified in Tables 1 and 2, as well as information outlined in Table 3
- For Aim 4B, survey instruments will be the source document for the variables outlined in Table 4. Video diaries will be obtained and stored, as detailed in section 5.5.

Table 1 (Data collected for all aims)

Blood Pressure readings at each outpatient clinic visit
Provider Name at each visit
Provider Specialty at each visit
Provider demographic
ICD-9/ICD-10 codes
Dates of each clinic visit
Patient insurance information
Patient date of birth
Patient ZIP Code
Patient age
Patient gender
Patient ethnicity
Patient BMI at each visit
Primary Care Physician Name and Practice Location
Patient glomerular filtration rate at each clinic visit
Highest A1C level during study period

Table 2 (Data collected for all aims)

ACE-Inhibitors/Angiotensin Receptor Blockers	Beta-Blockers	Diuretics	Calcium Channel Blockers	Nitrates	Other
Lisinopril	Metoprolol	Hydrochlorothiazide	Amlodipine	Imdur	Hydralazine
Benazepril	Bisporolol	Chlorthalidone	Diltiazem	Isordil	Clonidine

Captopril	Carvedilol	Metolazone	Verapamil		Aliskiren
Enalapril	Propranolol	Lasix	Felodipine		
Fosinopril	Nadolol		Isradipine		
Ramipril	Atenolol		Nifedipine		
Perinodopril	Labetalol				
Losartan	Nebivolol				
Valsartan					
Candesartan					
Irbesartan					
Telmisartan					
Azilsartan					
Eprosartan					
Olmesartan					

Table 3 (Data collected for Aim 3B only)

Initial Visit (Week 0)	Baseline blood pressure
	Current medications (names, doses and frequencies)
	Laboratory values (basic metabolic panel, TSH and A1C)
Weekly Phone Call (Weeks 1-8)	Record all uploaded blood pressures in the EMR
	New/updated laboratory values
	Current medications (names, doses and frequencies)
	Changes to medications (names, doses and frequencies)

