Aim 3B: Pilot study of the new time-to-control measure's responsiveness to more intensive blood pressure monitoring and intervention	
 1) Use of home blood pressure monitors linked the EMR will allow for weekly intervention by a clinical pharmacist, with titration of antihypertensive therapy, according the to 2017 ACC/AHA Hypertension Guidelines 2) The time-to-control period with will be shorter for those enrolled in the pilot study than those in the general population, not provided with home monitoring and weekly clinical pharmacist intervention
Aim 4A: Interview discussions to explore feasibility and acceptability intervention to increase blood pressure medication adherence	
 1) This is an exploratory aim, designed to inform Aim 4B. No a prior hypothesis.
Aim 4B: pilot study to measure the feasibility, acceptability, and efficacy of interventions designed to increase blood pressure medication adherence	
 1) Medication adherence and hypertension control will be greater among treatment groups compared to control group 2) Patients in the incentive group will demonstrate greater routinization compared to both the control group and the message group

For Aim 1, we will use these data to conduct descriptive analyses of rates of blood pressure control among patients with ambulatory care visits at Cedars-Sinai. Next, we will conduct multivariate regression models using blood pressure control as the outcome variable and various patient, physician and clinic characteristics as the independent variables. We will examine how results differ between the 2017 and JNC-7 guidelines.

For Aim 2, we will apply the new time-to-care measures and time-to-control measures to the same dataset. This will involve an iterative process of refinements as we discover issues that warrant the exclusion of certain blood pressure measurements, types of visits, or patient populations. The result will

be both refined measures and descriptive data on the time-to-care and time-to-control for both undiagnosed and uncontrolled hypertension.

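### The Section 4.0 rules for undiagnosed hypertension, new diagnosis and treatment initiation do not fit together, so treatment that precedes coding drops out of time-to-initiate

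*Protocol*

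**What the plan says.** All the rules stand together in Protocol Section 4.0.

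- **Undiagnosed hypertension:** two ambulatory readings at or above 130/80 "without an ICD-9/10 code for hypertension in the preceding year". Medication is not mentioned.
- **New diagnosis:** "an ICD-9/10 code for hypertension without a prior code or antihypertensive medication use in the preceding year".
- **Treatment initiation:** "the first prescription for an antihypertensive medication following a new diagnosis of hypertension".
- **Who is measured:** "time-to-diagnosis, for patients who qualify for new diagnoses; time-to-initiate, for the same patients".
- **What is measured:** days "from the last blood pressure above goal to the documentation of the diagnosis or the initiation/intensification of treatment".

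Section 2.0 gives the intent under Aim 2. The measures should show "how long it takes from when evidence exists in the EMR that patients meet criteria for hypertension" until a clinician documents the diagnosis and starts treatment, and so tell failure to recognise hypertension apart from failure to act on it.

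Section 7.1 foresees, for Aim 2, an "iterative process of refinements as we discover issues that warrant the exclusion of certain blood pressure measurements, types of visits, or patient populations". The SAP deals with the randomized text-message and incentive pilot and does not mention these measures.

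**The concern.** The entry state ignores medication, the new-diagnosis rule excludes on medication, and initiation depends on the new-diagnosis rule. A clinician who prescribes soon after the qualifying readings and enters the code later has both recognised the problem and acted on it. Under these rules the prescription comes too early to be an initiation, and it also disqualifies the later code as a new diagnosis. The measure then omits the care it was built to credit.

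The loss need not be even across clinics. Table 2 includes beta-blockers, diuretics and nitrates, which may be prescribed for other reasons, and patients taking them without a hypertension code may be more common in Cardiology and Nephrology. Section 7.1 (Aim 1 hypothesis 3 and Aim 3A hypothesis 3) sets those clinics, with Primary Care and Internal Medicine, against all others. The large sample in Section 7.2 does not remove an error that comes from a definition.

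**Working it through.** The plan gives no figure to reproduce here, so the check applies the three rules to example timelines. Day 0 is the second qualifying reading.

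**Rules as applied**
- Undiagnosed (U): no code in the 365 days before day 0.
- New diagnosis (N): a code on day c, with c at or after 0, no earlier code, and no antihypertensive use between day c − 365 and day c. The text allows two readings of the earlier-code condition: within the preceding year, or ever. Both were tried.
- Initiation (I): the first prescription on or after the day of N. A same-day prescription is allowed, which is the generous reading.

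| Timeline | U | N | I |
|---|---|---|---|
| A. Untreated; code day 60; drug day 60 | yes | 60 | 60 |
| B. Untreated; code day 60; drug day 90 | yes | 60 | 90 |
| C. Drug from day 30, continued; code day 60 | yes | none | none |
| D. Drug from day 30, continued; code day 500 | yes | none | none |
| E. Drug from day 30, continued; never coded | yes | none | none |
| F. Drug since day −500, continued; code day 60 or day 800 | yes | none | none |
| G. Drug days 30 to 60 only; code and new drug day 500 | yes | 500 | 500 |
| H. Drug day −500 to day 0; codes days 200 and 700; new drug day 700 | yes | 700 or none | 700 or none |
| J. Code day −800; no drug; code and drug day 60 | yes | 60 or none | 60 or none |

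In H and J the first entry holds if an earlier code counts only within one year, and the second if it counts at any time.

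**Reading the table**
1. A and B work as intended: coding comes first or on the same day.
2. C and D show the core fault. In C the code on day 60 looks back to day 60 − 365 = −305, finds the drug begun on day 30, and fails. With no new diagnosis, nothing can be an initiation. In D the drug is still being taken during the year before day 500, so the result is the same. Both hold under either reading of an earlier code.
3. E has prompt treatment and no code, and yields no event at all.
4. F is already treated, yet counts as undiagnosed. No later code or prescription produces an event while treatment continues.
5. G limits the claim. The patient is off drug for 500 − 60 = 440 days, more than 365, so both events return. The initiation is dated day 500 although the first prescription was on day 30.
6. H and J show that an older code, or a long gap in treatment, blocks the events on one reading only.

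The fault is therefore firm for patients who stay on treatment, and firm for time-to-initiate. For time-to-diagnosis it depends on the end point. If any documented code ends the clock, C ends on day 60, D on day 500, and F on day 60 or day 800. If only a new diagnosis as defined ends it, they have no event.

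**The case against.** **Entry.** Section 4.0 assigns both measures to patients who are eligible for a new diagnosis, not to the undiagnosed. On that reading an already treated patient never enters. This stands as a possible reading. Section 2.0 points the other way, since it starts from evidence in the record that criteria are met. If eligibility means later meeting the new-diagnosis rule, patients C and D are removed because of something that happened after their qualifying readings. The care is lost either way.

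**Planned refinement.** Aim 2 exists to develop these measures, and Section 4.0 promises a detailed study protocol and Advisory Board feedback. The refinement in Section 7.1, however, concerns exclusions. It could remove the already treated, but it gives no rule for counting a prescription that precedes the code.

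**Stronger readings that the documents do not support:**
- *Affected patients can never have the event.* G shows an exception, and time-to-diagnosis may end at any code.
- *Anyone with an old code is trapped.* J, untreated with an older code, has both events if the one-year limit governs codes as well as drugs.
- *Time-to-care is inflated.* Section 4.0 counts days to an event, and no censoring rule is given. A patient without an event has no value, which is a missing result and not a long one.
- *Time-to-initiate absorbs the coding delay.* A patient with a new diagnosis as defined had no antihypertensive in the year before, so the next prescription is normally the true start. G is the exception.
- *A size can be attached.* Assuming that 5% to 20% of flagged patients are affected, an undiagnosed rate of 20% would become 0.20 × 0.95 = 0.19 to 0.20 × 0.80 = 0.16 on an unchanged denominator, and a time-to-diagnosis curve would stop at 80% to 95%. The share has no source in the documents, and the 20% is a national rate used as a hypothesis in Section 7.1. A patient taking a Table 2 drug for another indication may be truly undiagnosed. The ceiling also needs the stricter end point, and no such curve is planned.

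**Conclusion.** The definitions conflict as written. A patient who is prescribed an antihypertensive after the qualifying readings, stays on it and is coded later has neither a new diagnosis nor an initiation. A continuously treated patient without a recent code is counted as undiagnosed and cannot have an initiation. Time-to-initiate thus omits prompt treatment given before coding. Time-to-diagnosis omits it too, if its end point is the defined new diagnosis.

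This rests on the literal wording of Section 4.0 and on continued treatment. Counting such patients as having entered the clock rests further on entry by blood pressure, which Section 2.0 supports. The number affected, and therefore the size of any bias, cannot be computed from the documents. The point bears on Aims 1 to 3A only. It should be settled before the measures are calculated, because it touches the distinction that Aim 2 is meant to draw.

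**What to change.** Reword Section 4.0 as follows.

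1. **Entry.** Patients enter time-to-diagnosis and time-to-initiate at the qualifying readings, with the same fixed one-year look-back for hypertension codes and for antihypertensive use. Those treated but uncoded at entry are reported as a separate group, not as undiagnosed. The clock-start wording should be aligned with this entry point.
2. **Time-to-diagnosis** ends at the first hypertension code after entry, whatever medication has been started since entry.
3. **Time-to-initiate** ends at the first antihypertensive prescription on or after the qualifying reading, coded or not.

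Under these rules C has an initiation on day 30 and a diagnosis on day 60. D has them on days 30 and 500. E has an initiation on day 30 and no diagnosis, which correctly shows action without documentation. F goes to the separate group.

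The look-back should stay fixed at one year. Looking back to any earlier date in the extract would give later patients a longer window, so fewer of them would count as undiagnosed for that reason alone. That could distort the comparison around the 2017 guideline in Section 7.1.

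The cost is wording and programming. Codes and visit dates are in Table 1, and Section 5.4 states that "Table 2 contains medications to be obtained at the patient level for each visit". The drawback is misclassification: some Table 2 drugs are given for other indications, so some patients will be placed in the treated group, or credited with an initiation, wrongly. Results should therefore be shown by clinic type, with and without the treated-but-uncoded group.

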4.0 STUDY DESIGN AND METHODS

Achieving these objectives and aims will involve an analysis of existing data from ambulatory care visits at clinics affiliated with Cedars-Sinai Medical Center from January 1, 2014 through March 30, 2019. Via a detailed study protocol, we will establish patient eligibility criteria, specify study variables and measures for extraction from the EMR, and specify descriptive and multivariate regression analyses

related to Aims 1-3. An Advisory Board consisting of local and national experts in EMR systems, population health, hypertension, and the implementation of quality improvement interventions will provide guidance and feedback on the protocol and after we have obtained preliminary data.

Patients will need to have at least two years of data available in CS-Link to be included in the study (defined as two or more clinic visits at least two years apart and occurring within the study dates). We will include ambulatory care visits with faculty, medical delivery network, and private physicians in all specialties if they use CS-Link. We will exclude care in the emergency department, urgent care, and hospital settings because blood pressure may be temporarily elevated due to acute illness. For eligible visits, we will obtain the recorded blood pressure values, whether the blood pressure was assessed manually or automatically (if available), and the physician identity (coded).

We will define blood pressure control based on the 2017 ACC/AHA guidelines (blood pressure <130/80). In sensitivity analyses, we will also consider control based on the JNC-7 guidelines (blood pressure <140/90), due to the recent change in the standard of care.

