5.2 TIME PERIOD OF DATA UNDER REVIEW

- Data will be reviewed from between the dates 1/1/2012 through 3/30/2019. For patients enrolled in the pilot study described in Aim 3B, data will be collected during the 9 week period of their participation.

- Data for Aims 1, 2 and 3A will be collected retrospectively. For Aim 3B, data will be collected weekly starting on the date of their in-person appointment and will be collected prospectively during the 9 week period of monitoring for each patient, estimated between the months of June and November, 2019. For Aim 4A, data will be collected during the interview discussions. For Aim 4B, data will be once per month during clinic visits for the first 3 months, and then every 3 months until 9 months after enrollment.
- Information will be kept for a total of 2 years following the initiation of the study.

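### The definitions of new and undiagnosed hypertension rest on a clear preceding year that need not be observed, so established hypertensives can be counted as new in their first year of record

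*Protocol*

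**What the plan says.** The measure definitions are in Protocol Section 4.0. A new diagnosis is an "ICD-9/10 code for hypertension without a prior code or antihypertensive medication use in the preceding year". Undiagnosed hypertension is two above-goal outpatient readings "without an ICD-9/10 code for hypertension in the preceding year"; this definition has no medication condition.

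New status decides who enters two of the care measures, "time-to-diagnosis, for patients who qualify for new diagnoses; time-to-initiate, for the same patients", and one of the two time-to-control measures. It also defines the start of treatment: "We will define treatment initiation as the first prescription for an antihypertensive medication following a new diagnosis of hypertension".

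The only record-length rule, also in Section 4.0, is "two or more clinic visits at least two years apart and occurring within the study dates". Section 3.2 separately asks for two visits in some 12-month period, not tied to any index event.

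The start date differs between sections. Section 4.0 analyses visits from 1 January 2014, while Section 5.2 states "Data will be reviewed from between the dates 1/1/2012 through 3/30/2019"; the Duration entry of the summary and Section 3.2 also start in 2012. No section calls 2012-2013 a look-back period. Section 7.1 models the measures by calendar quarter and looks for a change of intercept or slope after the 2017 guideline. The SAP covers only the Aim 4B trial.

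**The concern.** The absence of a code or prescription is informative only if someone was recording during that year. If the index event is the patient's first visit in the extract, the preceding year is empty and the condition is met automatically.

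Two cases show what follows.

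- A patient treated elsewhere for years is coded at the first visit in the record. With no earlier entry, this is a new diagnosis, and the next prescription, perhaps a renewal, counts as treatment initiation.
- An established patient has two above-goal readings in a specialty clinic that does not code hypertension. The patient counts as undiagnosed. If no antihypertensive has been recorded, a later primary-care code also counts as a new diagnosis and ends a time-to-diagnosis interval that reflects record entry rather than delay in care.

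At stake are the Aim 1 undiagnosed rate, which Section 7.1 compares with a national 20%, and time-to-diagnosis, time-to-initiate and time-to-control for new diagnoses. The Aim 3A quarterly series uses these measures.

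**Working it through.** The plan states no misclassification rate, so there is no figure to reproduce. The check has three steps.

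**1. Does the two-year rule protect the look-back?** It requires last visit minus first visit to be at least 2 years. An index event at the first visit satisfies it with 0 months of observed look-back. The rule leaves every patient time after the first year, but does not confine index events to that time.

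**2. Which quarters can contain first-year-of-record index events?** Inputs are the common end date of 30 March 2019, the two start dates and the two-year rule.

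- Quarters: 2014 start, 5 × 4 + 1 = 21; 2012 start, 7 × 4 + 1 = 29.
- Latest first visit of an eligible patient: 30 March 2019 − 2 years = 30 March 2017.
- Latest first-year-of-record index event: 30 March 2017 + 1 year = about 30 March 2018.

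| Quarters | 2014 start | 2012 start | 2012-2013 as look-back, index from 2014 |
|---|---|---|---|
| All index events in first year of record | 4 | 4 | 0 |
| Mixed | 13 | 21 | 17 |
| None possible (Q2 2018 to Q1 2019) | 4 | 4 | 4 |
| Total | 21 | 29 | 21 |

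If the series is split at the start of 2018, every earlier quarter can contain such events (16 of 16 for a 2014 start), against 1 of the 5 later quarters. The last column shows that an extract-level look-back alone does not remove this change, because patients still join until March 2017. A per-patient rule is needed as well.

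**3. What does an observed year achieve?** Suppose an established patient makes v visits in the look-back year and hypertension is coded at each with probability c, independently. The chance that the year shows no code is (1 − c)^v. The documents give no c; I assume 0.2 to 0.5. The value v = 6.67 is 500,000 visits ÷ 75,000 patients from Section 7.2. Both are lower bounds there, and it is not clear that the 75,000 is an annual count, so lower values are shown too.

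| v in look-back year | c = 0.2 | c = 0.4 | c = 0.5 |
|---|---|---|---|
| 0 (year not observed) | 1.00 | 1.00 | 1.00 |
| 1 | 0.80 | 0.60 | 0.50 |
| 2 | 0.64 | 0.36 | 0.25 |
| 4 | 0.41 | 0.13 | 0.06 |
| 6.67 | 0.23 | 0.03 | 0.01 |

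An unobserved year passes every established patient. An observed year screens out many, but not all where visits are sparse. Doubling the look-back squares each entry; for v = 2 and c = 0.4, 0.36² = 0.13. For a new diagnosis, the medication clause lowers the figures further for patients with a prescription in the observed record. For undiagnosed hypertension there is no such clause.

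**The case against.** Several points on the other side have force.

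- **Time-to-diagnosis is partly shielded.** Section 4.0 starts the clock at the last above-goal reading. A patient coded at the first visit has no earlier reading, so the interval may be undefined or near zero. The false interval needs an earlier above-goal reading without a code.
- **The medication clause helps.** Section 5.4 obtains medications for each visit, so a treated patient whose drug is recorded before the first code is not new. The clause cannot help when code and drug first appear together, and it does not apply to undiagnosed hypertension.
- **The undiagnosed measure is meant to find evidence that this EMR has not acted on.** That is a fair reading of Aim 2. It still does not make a patient under treatment elsewhere undiagnosed, nor make the Aim 1 rate comparable with a national one.
- **The 2012-2013 data could serve as look-back.** That would largely settle the first year of the extract, but no section says so, and later entrants remain exposed.
- **These aims develop the measures.** Section 4.0 promises a detailed protocol, and Section 7.1 allows iterative exclusions. Neither names a look-back, and a rule set before the results are seen is stronger than one chosen afterwards.

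A reader might go further and infer that new diagnoses are inflated many-fold, or that false cases crowd into the early quarters and build a trend of known direction into the Aim 3A series. The documents support neither. An inflation factor needs prevalence, incidence and coding rates that they do not give. It would also count first codes, whereas Section 7.1 models times and control rates.

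**Conclusion.** The gap is real. Applied as written, the Section 4.0 definitions can class established hypertensives as undiagnosed or newly diagnosed when the index event falls in their first year of record. This touches the Aim 1 undiagnosed rate and three of five Aim 2 measures: time-to-initiate and time-to-control for new diagnoses and, where an earlier above-goal reading exists, time-to-diagnosis.

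For Aim 3A, the documents' own dates establish that the scope for this error ends by about 30 March 2018, so the case mix of the new-diagnosis measures differs before and after the guideline change. Whether this lengthens or shortens the measured times, and by how many days, cannot be determined from the documents. Cross-sectional control rates do not depend on new status, and Aim 4B is unaffected. The probabilities in the second table rest on assumed coding rates and independent visits; they show the mechanism, not the size of the bias.

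**What to change.** In Section 4.0, require at least 12 months of observed outpatient record, with at least one visit in those 12 months, before any index reading or diagnosis used for undiagnosed hypertension or a new diagnosis. State also whether a prior code means any earlier code or only one in the preceding year.

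Reconcile the two start dates by declaring 2012-2013 as look-back, with index events from 1 January 2014. This keeps all 21 quarters. If the extract has to start in 2014, use its first 12 months for look-back only, which leaves 21 − 4 = 17 quarters.

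Add a sensitivity analysis with a 24-month look-back, because a 12-month rule leaves some misclassification where visits are sparse.

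The cost is an eligibility sentence, a date correction and programming on data that Section 5.2 already covers. Index events in each patient's first year are lost. The record-length condition alone excludes no patient, since the two-year rule leaves at least one further year; the visit condition will remove some index events after long gaps in care.

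### Every switch between antihypertensives counts as intensification, so a same-class replacement at an equal or lower dose level stops the time-to-intensify clock and biases the measure short

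*Protocol*

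**What the plan says.** Protocol section 4.0 creates "time-to-intensify, for patients with established diagnoses". The clock is the "number of days from the last blood pressure above goal to the documentation of the diagnosis or the initiation/intensification of treatment". The stopping event has three limbs. The first is "Treatment intensification will represent the addition of another antihypertensive medication"; the other two are "an increase in the dose of an existing antihypertensive medication, and a change from one antihypertensive medication to another". The third limb is not limited by class, dose or reason for the change.

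Section 2.0 (Aim 2) gives the purpose: to measure "how long evidence exists that control is suboptimal before clinicians intensify treatment". It adds that process and outcome measures together should show whether poor control comes from failure to recognise it, or from "lack of action (e.g., clinical inertia), or insufficient action (e.g., suboptimal adjustment of antihypertensive medications".

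Section 5.4 describes the medication extract behind Table 2: "Data is to include if the medication has been prescribed and if so, at what dose and frequency". Section 7.1 expects the measures to be refined as problems appear, and names the "exclusion of certain blood pressure measurements, types of visits, or patient populations". Medication events are not on that list. No sensitivity analysis of the switch limb is planned. The SAP covers only the adherence trial and does not use time-to-intensify.

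**The concern.** The first two limbs are increases in treatment. The third can be met by a change that is not an increase, such as one drug replaced by another of the same class at an equal or lower dose level, for reasons of tolerability, payer or supply. That patient leaves the risk set as though treatment had been intensified.

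Three uses of the measure are exposed:

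- **Level.** Time-to-intensify reads too short.
- **Comparisons.** Aim 3A relates the time measures to control rates by physician and clinic, compares clinic types, and looks for a change after the 2017 guideline. A background of neutral switches pulls real differences towards none. Section 7.1 predicts stable time-to-care after 2017, so dilution of a real slowing would favour the predicted result.
- **Interpretation.** A patient with a neutral switch and continued poor control is read as having had insufficient action, when no step had been taken to lower pressure.

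**Working it through.** **No plan figure to reproduce.** The documents give no time-to-intensify estimate and no switch rate. The figures below are an illustration on assumed rates.

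**Model.** True intensification occurs at a constant rate *a* and neutral switching at a constant rate *b*. The clock stops at whichever comes first.

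- Share of counted events that are not increases: b/(a+b)
- Measured median: ln 2/(a+b)
- Measured ratio between two settings whose true rates are a and a/2, with the same b in each: (a+b)/(a/2+b)

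**Assumed inputs.** a = 0.10 per month; b = 0.01, 0.03 or 0.05 per month. The true median is ln 2/0.10 = 6.9 months and the true ratio is 2.

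| b per month | Not increases | Measured median (months) | Measured ratio |
|---|---|---|---|
| 0.01 | 0.01/0.11 = 9% | ln 2/0.11 = 6.3 | 0.11/0.06 = 1.83 |
| 0.03 | 0.03/0.13 = 23% | ln 2/0.13 = 5.3 | 0.13/0.08 = 1.63 |
| 0.05 | 0.05/0.15 = 33% | ln 2/0.15 = 4.6 | 0.15/0.10 = 1.50 |

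The same ratios apply to a before-and-after comparison if the true rate halves from 0.10 to 0.05.

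**How strong the assumed rates are.** The yearly chance of a neutral switch is 1 − exp(−12b): 11%, 30% and 45%. The two upper values are high.

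**Second parameterisation.** Let s be the share of counted events that are neutral switches. Then the measured median = true median × (1 − s). For an assumed true median of 180 days and s = 5%, 10%, 20% or 30%, the measured median is 171, 162, 144 or 126 days. The proportion apparently intensified by 365 days is 77%, 79%, 83% or 87%, against a true 75.5%. Simulation with 400,000 draws per case agreed.

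**Unequal switching.** If two settings have the same a = 0.10 but b = 0.01 and 0.05, the measured ratio is 0.15/0.11 = 1.36 where the true ratio is 1. Dilution is therefore the result when b is equal; unequal b can create a difference.

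**What the literal rule admits.** Table 2 lists 38 drugs (15 + 8 + 4 + 6 + 2 + 3 by column), giving 38 × 37 = 1,406 ordered one-for-one switches. Within a named column, leaving out the column for other drugs, there are 15×14 + 8×7 + 4×3 + 6×5 + 2×1 = 310 (22%). The first column combines two classes, with 7 and 8 drugs, so 7 × 8 × 2 = 112 of the 310 cross between classes. That leaves 310 − 112 = 198 (14%) at most as same-class. These are counts of possible switches, not of how often they happen.

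**The case against.** **Inertia stays visible.** A reader might infer that the rule hides clinical inertia, or scores lack of action and insufficient action alike as adequate. The documents do not support that. Section 2.0 draws the distinction from process and outcome measures read together. A patient with no drug change has no intensification event, and one whose switch fails still has time-to-control running. What stands is narrower: a neutral switch moves some lack of action into insufficient action.

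**Reach of the wording.** A reader might also infer that replacing two drugs by one counts. The third limb describes one drug exchanged for another, so that case is not clearly covered. Nor does a shared Table 2 column mean like-for-like, given the mixed first column.

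**Some switches are real responses to high pressure.** This stands. For Aims 1 to 3A the reason for a change is not extracted, so a rule that excluded every switch without a higher dose level would discard genuine cross-class action and err the other way. It argues for a limited exclusion, not for leaving the limb open.

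**The measures are provisional.** Aim 2 exists to develop them, and section 4.0 provides for Advisory Board feedback after preliminary data. This mitigates the point, but the refinements named in section 7.1 do not include medication events.

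**The size is assumed.** This also stands. At b = 0.01 the effect is modest. The model takes constant rates from a fixed start, whereas the plan starts the clock at the last reading above goal. A burst of substitutions in one quarter, mimicking faster care, is possible but has no support in the documents.

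**Conclusion.** The point holds for same-class replacements at an equal or lower dose level. They end the clock without any increase in treatment, contrary to the purpose in section 2.0, and nothing in either document restricts them. The direction for the level is certain: time-to-intensify is biased short. Dilution of the Aim 3A comparisons follows if neutral switching is similar across settings and over time.

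The size cannot be established. On the assumed rates, a two-fold difference reads as 1.83 to 1.50 and the median falls from 6.9 months to between 6.3 and 4.6. Those figures treat all neutral switches as one rate; the same-class part, which is what can be identified from the extract, would account for only some of it.

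The scope is Aims 2 and 3A. Aim 3B uses time-to-control, and neither the Aim 4B trial nor the SAP is affected.

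**What to change.** As a measurement rule only, with no view on which treatment change is appropriate, amend the definition in section 4.0:

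1. Keep added drugs, dose increases and cross-class switches as events that end time-to-intensify.
2. Do not let a replacement within the same pharmacological class at an equal or lower dose level end the clock. Record it as a separate switch event. Define class pharmacologically, not by Table 2 column.
3. As a sensitivity analysis, report time-to-intensify with all switches counted and with none counted. The two results bracket the effect of neutral cross-class switches, which the extract cannot identify.
4. Fix the rule before the Aim 3A comparisons are run.

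**Cost.** A short within-class dose-level table, which the documents do not contain and which must be drawn up, and some programming on data already extracted. A few same-class switches prompted by high pressure will count only in the sensitivity analysis.
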